**8.6.2 Laboratory test values**

Descriptive statistics (except 2-sided 95% CIs of the mean) should be calculated by treatment group in each evaluation time point for hematology tests, blood biochemistry tests, C-reactive protein, and VEGF. Changes from the first day of the treatment period at each evaluation time point should also be summarized. As for qualitative urinalysis, a shift table which consists of frequency tabulation by category at each evaluation time point and the decision results on the first day of the treatment period and on each evaluation time point should be provided.

**8.6.3 Resting standard 12-lead ECG**

The frequency of each assessment result (normal, clinically nonsignificant abnormal, or clinically significant abnormal) should be tabulated at each evaluation time point, and a shift table, which consists of the decision results on the first day of the treatment period and each evaluation period, should be provided.

**8.6.4 Body weight (body weight excluding dialysate weight)**

Descriptive statistics (except 2-sided 95% CIs of the mean) should be calculated by evaluation time point. Changes from the first day of the treatment period at each evaluation time point should also be summarized.

**8.6.5 Vital signs**

Descriptive statistics (except 2-sided 95% CIs of the mean) should be calculated by evaluation time point for blood pressure and pulse rate. Changes from the first day of the treatment period at each evaluation time point should also be summarized.

**8.6.6 Fundoscopy**

The frequency of each decision result (normal, clinically nonsignificant abnormal, or clinically significant abnormal [Presence or absence of retinal hemorrhage, presence or absence of retinal edema]) should be tabulated at each evaluation time point, and a shift table, which consists of the assessment results (normal, clinically nonsignificant abnormal, or clinically significant abnormal), should be provided on the first day of the treatment period and each evaluation time point.

**8.6.7 Chest X-ray**

The frequency of each assessment result (normal, clinically nonsignificant abnormal, or clinically significant abnormal) should be tabulated at each evaluation time point, and a shift table, which consists of the assessment results on the first day of the treatment period and each evaluation period, should be provided.

**8.6.8 Proportion of subjects with documented Hb values of  $\geq 13.0$  g/dL or  $\geq 14.0$  g/dL**

The number and proportion of subjects with confirmed Hb values of  $\geq 13.0$  g/dL or  $\geq 14.0$  g/dL, after the first day of the treatment period, in each period between scheduled study visits and during the entire treatment period from the first day to Week 24 of the treatment period should be provided. If

Hb value is >13.0 g/dL and 14.0 g/dL in the same subject, the subject should be counted in both categories.

The similar analysis should be conducted for each patient cohort.

#### **8.6.9 Proportion of subjects with documented Hb values of <9.0 g/dL or <8.0 g/dL**

Subjects with confirmed Hb values of <9.0 g/dL or <8.0 g/dL should be analyzed in the same manner as in Section 8.6.8.

#### **8.6.10 Proportion of subjects with a documented Hb value increase rate of >0.5 g/dL/week**

The number and proportion of subjects in whom the Hb value increase rate is confirmed to be >0.5 g/dL/week, after the first day of the treatment period, in each period between scheduled study visits and during the entire treatment period from the first day to Week 24 of the treatment period should be provided. The Hb value increase rate in this tabulation should be calculated based on the difference in Hb values between the 2 time points measured on the scheduled study visit day in every 4 weeks (first day of the treatment period, Week 4, Week 8, Week 12, Week 16, Week 20, and Week 24 of the treatment period) and the Hb value measurement interval obtained from the actual study visit date. A similar analysis should be performed for each patient cohort. In addition, for the Conversion (Hb value <11.0 g/dL) cohort, the number and proportion of subjects in whom the Hb value increase rate calculated by the 2 methods defined in “4.13 Hb value increase rate” is confirmed to be >0.5 g/dL/week should also be provided.

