#### (2) Treatment period

The treatment period will last from completion of scheduled tests on the first day of the treatment period to completion of blood sampling for haematology tests on the final day of the treatment period (Week 24 of the treatment period or discontinuation of treatment).

Treatment period study visits will be made every 2 weeks up until Week 12, and every 4 weeks thereafter for scheduled tests. However, study visits may be more frequent if variation in Hb levels causes concern for excessive increase or decrease in Hb, or for other reasons.

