#### Dosage adjustment algorithm for MT-6548 Tablet

- ✓ Dosage increases are in principle separated by at least 4 weeks. There are no set intervals for dosage decreases, but frequent dosage adjustments are to be avoided.
- ✓ Decrease MT-6548 dosage by 1 tablet if Hb levels suddenly increase (more than 2.0 g/dL change in past 4 weeks\*).
- ✓ Increase MT-6548 dosage by 1 tablet if Hb levels are <11.0 g/dL. However, decrease by 1 tablet instead of increasing in cases of sudden increase in Hb (more than 2.0 g/dL change in past 4 weeks\*).
- ✓ Decrease MT-6548 dosage by 1 tablet if Hb is >12.5 g/dL.
- ✓ If Hb is >13.0 g/dL and ≤13.5 g/dL, and there has been a sudden increase in Hb (more than 2.0 g/dL change in past 4 weeks\*), discontinue MT-6548 administration and resume at 1 tablet reduced dosage after Hb falls to ≤13.0 g/dL.
- ✓ If Hb is >13.5 g/dL, discontinue MT-6548 administration and resume at 1 tablet reduced dosage after Hb falls to ≤13.0 g/dL.

\*Calculate Hb change rate using the Hb measurement closest to 4 weeks prior to the day of dosage adjustment (in the range of 3 to 5 weeks). A rate of change greater than 0.5 g/dL/week constitutes “sudden increase.” If Hb was not measured 3 to 5 weeks prior to the day of dosage adjustment, use the measurement made immediately prior to 5 weeks before the day of dosage adjustment.

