### 9.2.3 Efficacy endpoints

Blood sampling will be performed at each study center for measurement by the contract laboratory testing facility. All measurement results will be reported to each study center and the study sponsor.

(1) Hb value

Blood sampling and Hb measurement will be performed on the first day of the screening period, screening period Visit 2, the first day of the treatment period, Weeks 2, 4, 6, 8, 10, 12, 16, 20, and 24 of the treatment period, and the day of discontinuation of treatment.

(2) Ratio of subjects who received ESA rescue therapy

If ESA rescue therapy is performed, type of ESA formulation used, administration route, dose interval, and dosage will be recorded in the CRF.

(3) Ratio of subjects who received red blood cell (RBC) transfusion rescue therapy.

If RBC transfusion rescue therapy is performed, type of RBC formulation used and dosage will be recorded in the CRF.

(4) Study drug dosage

Study drug dosage will be recorded in CRFs.

(5) total number of dosage adjustments

Yes/no for MT-6548 dosage adjustments and post-adjustment dosage will be recorded in the CRF.

(6) Quantity of iron administered

Iron dosage will be recorded in CRFs.

(7) Ratio of subjects who received IV iron

Iron administration route will be recorded in CRFs.

(8) Iron-related measures (serum iron, TIBC, TSAT, and serum ferritin)

Blood sampling and measurement will be performed for serum iron, TIBC, TSAT, and serum ferritin on the first day of the screening period, the first day of the treatment period, Weeks 2, 4, 6, 8, 10, 12, 16, 20, and 24 of the treatment period, and the day of discontinuation of treatment.

(9) Hepcidin

Blood sampling and measurement of hepcidin will be performed on the first day of the treatment period, treatment period Weeks 2, 4, 6, 12, and 24, and the day of discontinuation of treatment.

(10) Haematocrit, RBC count

Blood sampling and measurement will be performed for haematocrit and RBC count on the first day of the screening period, the first day of the treatment period, Weeks 2, 4, 6, 8, 10, 12, 16, 20, and 24 of the treatment period, and the day of discontinuation of treatment.

(11) Reticulocytes (counts and fractions)

Blood sampling and measurement will be performed for reticulocytes (counts and fractions) on the first day of the screening period, the first day of the treatment period, Weeks 2, 4, 6, 8, 10, 12, 16, 20, and 24 of the treatment period, and the day of discontinuation of treatment.

(12) EPO

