## 4.13 Hb value increase rate

The Hb value increase rate is defined as the rate calculated using the following method.

✓ Hb value increase rate (g/dL/week):

$(\text{Hb value at Week 4 of the treatment period} - \text{Hb value at the start of the treatment period}) / ((\text{Hb value measurement day at Week 4 of the treatment period} - \text{Hb value measurement day at the start of the treatment period}) / 7)$

✓ Hb value increase rate (regression) (g/dL/week):

The slope of the regression line calculated based on the Hb values measured from the first day of the treatment period to Week 6 of the treatment period and the measurement day (weeks from the first day of the treatment period) is defined as the Hb value increase rate (regression). Subjects without data at the first day and Week 6 of the treatment period should be excluded from the tabulation. The number of weeks from the first day of the treatment period used to obtain the regression line is defined by the following formula.

First day of the treatment period: 0

Week 2 of the treatment period:  $(\text{Measurement day at Week 2 of the treatment period} - \text{the first day of the treatment period}) / 7$

Week 4 of the treatment period:  $(\text{Measurement day at Week 4 of the treatment period} - \text{the first day of the treatment period}) / 7$

Week 6 of the treatment period:  $(\text{Measurement day at Week 6 of the treatment period} - \text{the first day of the treatment period}) / 7$

Unscheduled study visit from the first day of the treatment period to Week 6 of the treatment period:  $(\text{Day of unscheduled study visit} - \text{the first day of the treatment period}) / 7$

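### SAP 8.6.10 takes its main Hb rate of rise from a fixed 4-weekly grid, so a rise above 0.5 g/dL/week over Weeks 2–6 or 6–10 can go uncounted

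*SAP*

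**What the plan says.** The protocol lists the share of subjects whose Hb rises faster than 0.5 g/dL/week as a safety endpoint (5.3.2), and the rationale there ties it to excessive or acute rises. Protocol 13.3.3 (4) says only that numbers and ratios will be shown. It sets no interval and no set of visits.

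SAP 8.6.10 supplies the rule. The main rate is the difference between two Hb values "measured on the scheduled study visit day in every 4 weeks", listed as "first day of the treatment period, Week 4, Week 8, Week 12, Week 16, Week 20, and Week 24 of the treatment period", divided by the actual interval. Results are wanted "in each period between scheduled study visits and during the entire treatment period". For the Conversion (Hb <11.0 g/dL) cohort alone, the section also counts subjects "in whom the Hb value increase rate calculated by the 2 methods defined in" SAP 4.13. The regression rate there takes in Weeks 2, 4 and 6 and any "Unscheduled study visit from the first day of the treatment period to Week 6 of the treatment period".

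Central-laboratory Hb is available at "Weeks 2, 4, 6, 8, 10, 12, 16, 20, and 24 of the treatment period" (Protocol 9.2.3), and Protocol 5.2 (2) allows that "study visits may be more frequent if variation in Hb levels causes concern for excessive increase or decrease in Hb". The dose-adjustment section (Protocol 8.3) applies the same 0.5 g/dL/week threshold with a rolling look-back: "Calculate Hb change rate using the Hb measurement closest to 4 weeks prior to the day of dosage adjustment", within a range of 3 to 5 weeks.

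**The concern.** An endpoint meant to detect acute rises leaves out three of the seven scheduled on-treatment Hb values up to and including Week 10 or 12 visits, namely Weeks 2, 6 and 10. A 4-week rise that straddles two grid windows is split between them, and each half can fall below the threshold. Unscheduled central-laboratory values are not used either, although the protocol foresees extra visits when an excessive Hb change is feared.

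Adding windows to the grid can only leave the count unchanged or raise it. The omission therefore acts in one direction, towards a lower reported proportion in a safety table. At the planned 40 subjects, one missed subject is 1/40 = 2.5 percentage points.

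The section also has an internal mismatch. Scheduled visits are two weeks apart up to Week 12, and SAP 4.10 counts the periods between them as 14 days there. A 4-weekly difference cannot fill a 2-weekly row.

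**Working it through.** **1. The threshold.** Protocol 8.3 gives it both as more than 2.0 g/dL in 4 weeks and as more than 0.5 g/dL/week. 2.0 / 4 = 0.5, so the two agree. A window of about 4 weeks is thus the protocol's own and is not at issue. The difference is fixed versus rolling windows.

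**2. A rise over Weeks 2–6.** Take Hb 10.0 at Day 0 and Week 2, 11.1 at Week 4, and 12.2 from Week 6 on.
- Weeks 2–6: (12.2 − 10.0) / 4 = 0.55, above the threshold.
- Grid, Weeks 0–4: (11.1 − 10.0) / 4 = 0.275.
- Grid, Weeks 4–8: (12.2 − 11.1) / 4 = 0.275.
- All later grid windows: 0. The subject is not counted.

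The same shape moved to Weeks 6–10 gives 0.275 in Weeks 4–8 and in Weeks 8–12, and is also missed.

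**3. Do the SAP 4.13 rates catch it?** For the Week 2–6 case:
- Week 4 method: (11.1 − 10.0) / 4 = 0.275.
- Regression on weeks 0, 2, 4, 6 (deviations −3, −1, 1, 3; sum of squares 20): (−30 − 10 + 11.1 + 36.6) / 20 = 7.7 / 20 = 0.385.

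Both are below 0.5. For the Week 6–10 case Hb is flat up to Week 6, so both are 0.

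**4. How much could the omitted windows matter?** This needs assumptions. Suppose a noise-free linear rise at rate r, lasting 4 weeks, with a start spread evenly over Weeks 0–8. A window starting at week a averages r × (4 − |s − a|) / 4 for a rise starting at week s. This exceeds 0.5 when |s − a| < d, where d = 4 × (1 − 0.5 / r). Grid windows start at 0, 4 and 8, so they cover 4d of the 8 weeks. Adding starts at 2 and 6 covers 8d, capped at 8.

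| r (g/dL/week) | d (weeks) | Grid detects | Grid plus Weeks 2–6 and 6–10 |
|---|---|---|---|
| 0.55 | 0.364 | 18% | 36% |
| 0.60 | 0.667 | 33% | 67% |
| 0.70 | 1.143 | 57% | 100% |
| 0.80 | 1.500 | 75% | 100% |

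Simulation of 200,000 paths per row agrees with these figures to within rounding.

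**5. Noise.** With no true rise and independent variation around a stable Hb (assumed SD 0.2–0.5 g/dL), simulation wrongly counts 0–1.4% of subjects on the grid and 0–1.8% with the two added windows. Using every adjacent scheduled pair, which is 2-weekly to Week 12, wrongly counts 0.1–41.7%.

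**6. Do the added pairs keep the protocol's interval?** Table 9.1-1 permits Week 2 on Days 11–17, Week 6 on Days 39–45 and Week 10 on Days 67–73. Weeks 2–6 are then 39 − 17 = 22 to 45 − 11 = 34 days apart, and Weeks 6–10 are 67 − 45 = 22 to 73 − 39 = 34 days apart. Both lie inside 21–35 days. Some grid pairs need not: Week 16 (Days 105–119) to Week 20 (Days 133–147) can be 14 to 42 days.

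**The case against.** The SAP does not contradict the protocol, which sets no interval for this endpoint. Fixed, non-overlapping 4-week windows match the dosing section's window length and limit repeated looks at noisy data. The endpoint is descriptive, in an uncontrolled study, and no decision rule hangs on it. Other tables also bear on excessive Hb: counts at or above 13.0 and 14.0 g/dL (SAP 8.6.8), Hb and its change at each visit with individual time courses (8.5.1), and Hb around dose reductions or interruptions (8.6.11). All of this stands, and it limits the weight of the point. None of it counts subjects by rate of rise over the missing windows.

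Several stronger readings are tempting but unsupported:
- **That the rate is computed only on the grid.** The Conversion (Hb <11.0 g/dL) cohort also gets the SAP 4.13 rates.
- **That a definite share of rapid risers is lost.** The documents give no within-subject SD and no expected rate. Under assumed SDs of 0.6–1.0 g/dL, 2-week autocorrelation of 0.7–0.8 and measurement SD of 0.2, simulation with no true rise already leaves 20–26% of flagged subjects off the grid. Much of any such figure comes from counting eight windows instead of six (2/8 = 25%).
- **That the table should reproduce the dosing algorithm's flags.** Those rest in principle on HemoCue values, which Protocol 8.3 bars from efficacy and safety analysis. The shared element is the definition, not the measurements.
- **That the early weeks carry the most risk.** The documents do not say so.
- **That every 2-week pair should count.** Step 5 shows that this would largely count noise.

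**Conclusion.** The point holds as a modest gap in a safety tabulation. By arithmetic alone, the main rate in SAP 8.6.10 can miss a rise over Weeks 2–6 or 6–10 that meets the protocol's stated rate definition, and the supplementary rates do not close the gap. The Conversion (Hb ≥11.0 g/dL) cohort has only the fixed grid.

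The size in this trial is unknown. The detection figures (18–75% on the grid against 36–100% with two added windows) describe an assumed noise-free 4-week rise of 0.55–0.80 g/dL/week starting in Weeks 0–8. They are not estimates for these subjects. Whether the result is called an undercount depends on taking the protocol's rolling window as the reference. After Week 12 scheduled visits are themselves 4-weekly, so only unscheduled values can be lost there.

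**What to change.** Keep the prespecified fixed-grid result as it is. Add one row, for all subjects and by cohort, that counts a subject if the rate exceeds 0.5 g/dL/week in any of:
- a fixed-grid pair;
- the Week 2–6 or Week 6–10 pair;
- a pair 3–5 weeks apart that includes an eligible unscheduled central-laboratory Hb.

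HemoCue values stay out. The new pairs must be added to the grid, not put in its place. A rule limited to 3–5 weeks would drop some grid pairs that Table 9.1-1 permits, and the count could then fall.

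State in 8.6.10 which reporting periods the 4-weekly rate can fill, for example by tabulating it by 4-week window, and reconcile this with the request for every period between scheduled visits.

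Record the row and its reason as an addition under Protocol 13.4. If the data are already locked, show it separately from the original plan, as that section requires.

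The cost is a little programming on data already collected, a count equal to or higher than the fixed grid, and slightly more noise-driven counts (0–1.8% against 0–1.4% under the assumptions in the check).

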#### **8.6.11 Summary statistics of Hb values before and after dose reduction or drug interruption**

Descriptive statistics of Hb values at dose reduction / interruption and after dose reduction / interruption of the study drug should be calculated. In addition, the change in Hb value after dose reduction / interruption of the study drug should be determined, and descriptive statistics should be calculated.

For the Hb value after dose reduction / drug interruption of the study drug, the data of the day closest to 4 weeks (28 days) after the Hb value measurement day at dose reduction / drug interruption should be adopted. If no study drug data at the time of dose reduction / drug interruption are available, subjects should be excluded from the Hb value analysis. In addition, the interval (days) from the Hb value measurement in dose reduction / interruption of the study drug to the Hb value measurement after dose reduction / interruption should be calculated, and the descriptive statistics should be provided.

A similar analysis should be performed for each patient cohort.

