##### (1) ESA formulations

If a subject has received maximum dosages of MT-6548 for  $\geq 2$  weeks and meets all criteria below, investigators/subinvestigators may administer ESA as rescue therapy to improve Hb levels if necessary in order to secure subject safety. ESA rescue therapy may also be administered without meeting the criteria below if deemed necessary by investigators/subinvestigators in order to secure subject safety, such as in cases of acute decreases in Hb. MT-6548 administration will be discontinued if implementing ESA rescue therapy. Study drug treatment may resume if Hb levels improve, as long as there is no concomitant use with ESA. Subjects who are not expected to resume study drug treatment will

be withdrawn from the study.

- ✓ Anaemia or anaemia symptoms (e.g., fatigue, weakness, shortness of breath, chest pain, confusion, dizziness) become aggravated compared to the first day of the treatment period to the point they are clinically problematic.
- ✓ Hb levels drop to <8.0 g/dL.

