#### 3.2 Safety endpoints

- (1) Adverse events and adverse drug reactions
- (2) Laboratory test values
  - 1) Hematology tests:

Mean corpuscular volume, mean hemoglobin, mean hemoglobin concentration, RBC distribution width, WBC count, WBC fractions (neutrophils, eosinophils, monocytes, lymphocytes, basophils), platelet count

- 2) Blood biochemistry tests:

Total protein, albumin, blood glucose, urea nitrogen, creatinine, uric acid, CPK, total bilirubin, AST, ALT, ALP, LDH,  $\gamma$ -GTP, Na, K, Cl, Ca, P, Mg, bicarbonate, total cholesterol, LDL-C, HDL-C, triglycerides

- 3) C-reactive protein
  - 4) Folic acid and vitamin B12
  - 5) Vascular endothelial growth factor (VEGF)
  - 6) Urinalysis (qualitative)
- Glucose, protein, urobilinogen, occult blood
- (3) Resting standard 12-lead ECG
  - (4) Body weight (body weight excluding dialysate weight)
  - (5) Vital signs
  - (6) Fundoscopy
  - (7) Chest X-ray
  - (8) Proportion of subjects with documented Hb values of  $\geq 13.0$  g/dL or  $\geq 14.0$  g/dL
  - (9) Proportion of subjects with documented Hb values of  $< 9.0$  g/dL or  $< 8.0$  g/dL.
  - (10) Proportion of subjects with a documented Hb value increase rate of  $> 0.5$  g/dL/week
  - (11) Hb value after dose reduction or interruption of the study drug

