## **7.3 Handling of efficacy endpoints if rescue therapy is performed**

If rescue therapy is performed, data from the day after rescue therapy should not be used for efficacy analysis.

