## 8.6 Safety analysis

The safety analysis population should be analyzed. When necessary, frequency and proportion should be calculated for discrete variables and descriptive statistics for continuous variables. Unless otherwise specified, no analysis will be performed for each patient cohort.

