**8.6.1.7 Adverse events before and after drug interruption**

The number of subjects and incidence rate should be calculated for adverse event and adverse drug reaction by before and after drug interruption for the overall and for individual events classified by SOC and PT. It should be classified to 2 categories: 4 weeks before drug interruption and 4 weeks after drug interruption (4 weeks after the start of drug interruption). If a subject had multiple drug interruptions and the adverse event occurred within 4 weeks after the drug interruption and within 4 weeks before the drug interruption, the subject should be counted as 1 subject for both periods.

Drug interruption period is defined as the "Planned start date of the modified dose" when "Yes" was selected in the query of "Did you choose the dosage according to the dosage adjustment algorithm?" and "Changed dose" = 0 mg in the query of "Whether the dose was changed" in the "Administration status of MT-6548" of the case report form. If "No" is selected for the query of "Did you choose dosage according to dosage adjustment algorithm?", the subject should not be included in the tabulation.

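### SAP 8.6.11 pools Hb after every dose reduction or interruption, so any interruption for ESA rescue would mix ESA-raised Hb with Hb after reductions or stops for high Hb

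*SAP*

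**What the plan says.** SAP 3.2 lists as safety endpoint (11): "Hb value after dose reduction or interruption of the study drug". SAP 8.6.11 puts it into practice: "Descriptive statistics of Hb values at dose reduction / interruption and after dose reduction / interruption of the study drug should be calculated". It also asks for the change in Hb. For the later value it takes "the data of the day closest to 4 weeks (28 days) after the Hb value measurement day at dose reduction / drug interruption". Its one exclusion is for missing data at the time of the reduction or interruption, in which case "subjects should be excluded from the Hb value analysis". The interval between the two measurements is summarised, and the analysis is repeated by patient cohort. Neither the reason for the dose change nor rescue therapy is mentioned.

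SAP 8.6 gives the population: "The safety analysis population should be analyzed". The rule on rescue is in SAP 7.3: "data from the day after rescue therapy should not be used for efficacy analysis". SAP 8.5 and Protocol 13.2 (3) say the same, again for efficacy alone.

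On stopping the drug, the algorithm in Protocol 8.3 reduces or stops MT-6548 for high or fast-rising Hb. Protocol 8.5.3 (1) adds a second route: "MT-6548 administration will be discontinued if implementing ESA rescue therapy". Treatment may resume if Hb improves, provided ESA is not used at the same time.

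**The concern.** Two kinds of event that start from opposite ends of the Hb scale fall into one summary. After a reduction or stop for high or fast-rising Hb, one expects Hb to fall. After a stop for ESA rescue, Hb is usually low at the start and one expects it to rise, because of the ESA. A mean over both describes neither group. A reader of the safety table wants to know what Hb does once the dose is lowered or stopped, and could conclude that it falls less than it does. Transfusion within the 28 days acts in the same direction as ESA. Phlebotomy acts the other way and would make the fall look larger.

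The neighbouring analysis of adverse events around interruptions, SAP 8.6.1.7, does separate events: when the dose was not chosen under the algorithm, "the subject should not be included in the tabulation". SAP 8.6.11 neither repeats nor cites that restriction, so the two before-and-after analyses treat the same interruptions differently without comment.

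**Working it through.** SAP 8.6.11 gives no figure to reproduce. The only design figure is the precision of mean Hb: t(0.975, 39) × 1.78/√40 = 0.569, which agrees with the stated 0.57 g/dL. It has no bearing on this point.

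**Can the mixing occur under the text?**
1. Is an ESA-rescue stop an interruption? SAP 4.6 starts an interruption at the first CRF entry of a 0 mg daily dose and names no reason. The errata change only how its end date is set. So it is, if the site enters 0 mg.
2. Can a later Hb exist? Protocol 8.5.3 lets rescued subjects stay in the study and resume. SAP 8.6.11 sets no window around day 28, so the nearest available value serves.
3. Is there time for it? The criteria-based route needs at least 2 weeks at the maximum dose. From 300 mg, that takes two one-tablet increases, in principle at least 4 weeks apart. With a first increase at Week 2, the route opens at about Week 2 + 4 + 2 = 8, and a value 4 weeks later falls at Week 12 of 24. Rescue outside the criteria is also allowed and can come earlier.
4. Does another rule remove the value? The post-rescue exclusions cover efficacy, and 8.6.11 is a safety analysis.
5. Does the cohort split separate the groups? No. SAP 6 defines cohorts by prior ESA and screening Hb, not by reason for stopping.

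**How large could it be?** The documents give no event counts and no expected changes, so every input below is an assumption. Let a be the 4-week change after a high-Hb event (−1.0 to −1.5 g/dL), b the change after an ESA-rescue stop (+1.0 to +2.0 g/dL), and p the share of rescue stops (0 to 30%).

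Pooled mean change = (1 − p)·a + p·b. Fraction of the fall hidden = p·(b − a)/(−a).

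| a | b | p = 0 | 5% | 10% | 20% | 30% |
|---|---|---|---|---|---|---|
| −1.0 | +1.0 | −1.00 | −0.90 | −0.80 | −0.60 | −0.40 |
| −1.0 | +2.0 | −1.00 | −0.85 | −0.70 | −0.40 | −0.10 |
| −1.5 | +1.0 | −1.50 | −1.375 | −1.25 | −1.00 | −0.75 |
| −1.5 | +2.0 | −1.50 | −1.325 | −1.15 | −0.80 | −0.45 |

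At p = 10% the hidden part runs from 0.1 × 2.5/1.5 = 17% to 0.1 × 3.0/1.0 = 30%. At p = 20% it runs from 33% to 60%. At p = 0 it is nil. The sign reverses only when p exceeds −a/(b − a), which on these inputs lies between 1.0/3.0 = 33% and 1.5/2.5 = 60%.

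The mean Hb at the time of the change moves down as well. Taking the protocol's thresholds as stand-ins (12.5 or 13.5 g/dL for high Hb, 8.0 g/dL for rescue), a 10% share lowers it by 0.1 × 4.5 = 0.45 to 0.1 × 5.5 = 0.55 g/dL.

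**The case against.** The strongest reply is that a description of Hb after every reduction or interruption, whatever the reason, is a legitimate safety summary. The SAP makes no claim about a drug-withdrawal effect and plans no test here. This stands. A reader might infer that the plan sets out to estimate such an effect and estimates it wrongly, but neither SAP 3.2 nor 8.6.11 says so.

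A reader might also infer that ESA-raised Hb certainly enters the table and hides a known share of the fall. The documents do not support that. It needs a rescued subject, a 0 mg entry and a later Hb. Criteria-based rescue also requires Hb below 8.0 g/dL with clinically problematic worsening, and subjects not expected to resume are withdrawn. With about 40 subjects the count may be zero. Transfusion and phlebotomy are not tied to a drug stop at all and matter only if given in the window.

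Other outputs help in part. SAP 8.1.2 includes the median, minimum and maximum, 8.2.2 tabulates interruptions by reason, and 8.5.2 (3) counts rescue. None of these links the reason to the Hb change. The individual Hb plots in 8.5.1 (2) are efficacy outputs, so under the rule in 8.5 they would omit post-rescue values. The lists of output tables in the SAP's contents were not available for this review, so a split by reason there cannot be ruled out.

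The definition in 8.6.1.7 might be thought to carry over, but its wording confines it to its own tabulation. Importing its filter would also be a poor remedy. Protocol 8.3 allows off-algorithm adjustments for safety, and those events would drop out of a safety table.

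**Conclusion.** The gap is real and conditional. Followed as written, SAP 8.6.11 would pool ESA-raised Hb with Hb after reductions or stops for high or fast-rising Hb whenever a rescue interruption has a later Hb. Neither the errata nor any other section of the supplied text prevents this. The direction is clear: toward zero or upward for ESA and transfusion, downward for phlebotomy. The size is unknown and may be zero. The 17% to 30% at a 10% share rests on assumed changes and an assumed share. This is a cheap improvement to one descriptive safety table and leaves the primary endpoint untouched.

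**What to change.** In SAP 8.6.11, keep all reductions and interruptions, but tabulate Hb at the event, Hb after it, and the change by the reason recorded in the CRF: high or rising Hb under the algorithm, ESA rescue, adverse event, other. Say how an event with several reasons is counted, since 8.2.2 allows more than one. Show follow-up Hb taken after ESA, transfusion or phlebotomy in the 28-day window separately, or flag those values and add a sensitivity summary without them. State that the algorithm-only filter of 8.6.1.7 is not used to drop events here, so that off-algorithm safety reductions stay visible.

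No new data are needed. Protocol 9.2.2 collects reasons for dose changes and drug holidays, and 8.5.3 requires rescue details in the CRF. If the CRF has no code for ESA rescue as a reason, it can be derived from the rescue records. The cost is smaller cells per reason and a little more programming. If the data are already locked, Protocol 13.4 allows the split as an added analysis, with its reason stated and its results kept distinct from the original plan.
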